9.6 Concomitant Medications

Number and proportion of patients taking concomitant medications prior to Treatment Phase, during Treatment Phase, and after study therapy are tabulated by drug classification and medication preferred name using the WHO drug dictionary.

9.7 Extent of Exposure

The start date of double-blind IMP will be the first day of double-blind dosing. The number and percentage of patients who receive brexpiprazole will be presented by 4-week interval. This summary will be performed on the Safety Sample, and will also be done by ADT.

The number and percentage of patients who receive each dose of brexpiparzole (0.5mg/day, 1mg/day, 2mg/day and 3mg/day) will be summarized by 4-week interval. This summary will also be done by ADT.

The number and percentage of patients who receive ADT medications will also be summarized by ADT.

9.8 Other Safety Data

Descriptive statistics will be provided for the SAS, AIMS, BARS, and MSFQ scales. Change from baseline in body weight will be summarized by descriptive statistics, as well as incidence of clinically significant changes in body weight. Descriptive statistics will also be provided for change from baseline in waist circumference and BMI.

Descriptive statistics will be summarized at each visit using the OC data set and at the last visit (Week 52/ET) using the LOCF data set.

9.8.1.1 Post-baseline concomitant Medications

Concomitant medications used post-baseline will be summarized in 2 categories of time interval - during IMP treatment period and after IMP treatment period. In each case, use of concomitant medication will be summarized by number and percentage of users.

10 Other Outcomes

The percentage of subjects hospitalized for exacerbation of symptoms (including emergency department visits) will be tabulated as a measure of healthcare resource utilization. The frequency of outpatient visits to various healthcare providers (eg, primary care physician, psychiatrists, other mental health practitioners, etc.) not required per the protocol will also be examined.

11 Conventions

11.1 Study Visit Windows

Study visit windows will be used to map visits using study day intervals. This visit window convention applies to tables and listings for all efficacy and safety scales (CGI-S, CGI-I, SDS, IDS-SR, SAS, AIMS, BARS and MSFQ). This derived study window variable will be named as WEEK and will be footnoted. In listings it will be listed along with the CRF study visit.

Table 11.1-1 shows classifications for study day intervals. The variable “target day” is defined using the number of days since the start of open-label OPC dosing in the study. The first day of open-label OPC dosing is defined as “Day 1”. If more than one observation falls within a particular study day interval, then the last observation within that interval is used. Evaluations occurring more than seven days after the last dosing date will be excluded from the analysis.

Table 11.1-1 Study Day and Visit Windows		
Week	Target Day ^a	Study Day Interval ^a
1	7	2-10
2	14	11-21
4	28	22-35
6	42	36-49
8	56	50-77
14	98	78-119
20	140	120-161
26	182	162-203
32 ^c	224	204-245
38 ^c	266	246-287
44 ^c	308	288-336
52 ^c	364	337-385 ^b

^a Relative to the first day of open-label OPC dosing.

^b Evaluations occurring more than seven days after the last OPC dosing will be excluded from summaries of change from baseline analyses.

^c Evaluations The duration of the length of the treatment phase was reduced to 26 weeks in Protocol Amendment 3. Therefore, the 26-week enrollers didn't have these visits.

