1.2 Clinical Studies

1.2.1 Pharmacokinetics/Pharmacodynamics

The pharmacokinetics of single and multiple doses of brexpiprazole was studied in healthy subjects and in subjects with MDD, attention-deficit/hyperactivity disorder (ADHD), and schizophrenia or schizoaffective disorder. Based on preclinical data and human clinical trials, brexpiprazole (OPC-34712) and one metabolite, DM-3411, were identified as the major analytes that are present in human plasma. *In vitro*, the activity of DM-3411 is 17 times lower than that of brexpiprazole and thus is considered as an inactive metabolite. Both brexpiprazole and DM-3411 pharmacokinetics were linear following single oral doses of brexpiprazole 0.2 to 8 mg to healthy subjects. The

terminal phase elimination half-life of brexpiprazole and DM-3411 was 48.3 to 80.8 hours and 48.6 to 77.5 hours, respectively. The median time to maximum (peak) plasma concentration (t_{max}) occurred at approximately 2 to 6 hours postdose for brexpiprazole and at approximately 10 to 24 hours postdose for DM-3411. In healthy subjects, administration of single-dose brexpiprazole with a high-fat meal did not affect its rate and extent of absorption.

Steady state pharmacokinetics also appeared to be linear following multiple daily doses of brexpiprazole in the range of 0.5 to 2 mg to healthy subjects. The accumulation factor based on maximum (peak) plasma concentration (C_{max}) and area under the concentration-time curve calculated to the last observable concentration at time t (AUC_t) was approximately 4 times. After multiple dose administration of brexpiprazole (1 to 12 mg/day) to subjects with schizophrenia or schizoaffective disorder, brexpiprazole and DM-3411 mean terminal elimination half-life at steady state was 95.4 and 89.3 hours, respectively; median t_{max} was 3.0 and 8.0 hours, respectively.

In drug interaction trials in healthy subjects, brexpiprazole was shown to be metabolized by CYP3A4 and CYP2D6 isozymes and was not an inhibitor of CYP3A4, CYP2B6, CYP2D6, or P-glycoprotein. Coadministration of potent CYP3A4 or CYP2D6 inhibitors with brexpiprazole resulted in about a 2-fold higher exposure and about a 1.5-fold increase in the terminal elimination half life of brexpiprazole. Of note, administration of brexpiprazole with fluoxetine, paroxetine, or duloxetine (MDD medications coadministered in this trial) may potentially increase brexpiprazole plasma concentrations by up to 2-fold.

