3.6.1.9 Follow-up

Follow-up safety information (AEs and concomitant medications) will be collected 30 (+ 2) days after the last dose of open-label medication for all subjects (completers and early withdrawals). Follow-up information can be obtained via telephone contact or clinic visit at the investigator’s discretion.

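### The 7-day post-dose cut-off in SAP 11.1 also removes late safety-scale ratings, can leave early leavers with no analysed AIMS or MSFQ, and is worded two ways

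*SAP*

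**What the plan says.** SAP 11.1 maps assessments to visit weeks and sets the scope of that convention: "This visit window convention applies to tables and listings for all efficacy and safety scales". The scales listed are CGI-S, CGI-I, SDS, IDS-SR, SAS, AIMS, BARS and MSFQ. C-SSRS and adverse events are not listed. The section then sets the cut: "Evaluations occurring more than seven days after the last dosing date will be excluded from the analysis". No reason is given for seven days.

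Footnote b of Table 11.1-1 in the same section is narrower: "Evaluations occurring more than seven days after the last OPC dosing will be excluded from summaries of change from baseline analyses". Its marker sits on the Week 52 row, a visit that 26-week enrollers do not have.

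The observed-case and LOCF definitions (Protocol 7.1.1; SAP 5.1 and 5.2) contain no such cut. SAP 5.2 does not allow baseline to be carried forward. SAP 9.8 summarises the safety scales by visit on observed cases and at the last visit on LOCF.

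Protocol 3.7.3 requires subjects who withdraw before Week 26 to have their ET evaluations when they withdraw. Protocol 3.6.1.8 softens this to where possible.

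**The concern.** Long-term safety and tolerability is the primary objective, and the four scales are named safety variables. One cut is applied to efficacy and safety scales alike, although the reason for stopping the clock differs. An efficacy score off drug says little about benefit on drug. A movement or sexual-function rating shortly after stopping may still reflect the drug.

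The current schedule makes this more than a matter of a few lost records. AIMS and MSFQ are rated so seldom after baseline that excluding one late ET rating can leave a subject with nothing to analyse. The subjects exposed to this are early leavers, so the AIMS and MSFQ tables could rest more heavily on subjects who stayed. Separately, two programmers working from the text and from footnote b could build different datasets.

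**Working it through.** **Which ratings can be lost**

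The schedule is Protocol Table 3.6-1 (Amendment 4). The case is a subject who stops early and whose ET visit falls more than 7 days after the last dose.

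| Scale | Post-baseline ratings | Left after the late ET rating is excluded |
|---|---|---|
| SAS, BARS | Weeks 1, 2, 4, 8, 14, 20, 26/ET | Rating from the last visit attended before stopping |
| AIMS | Weeks 14, 26/ET | Week 14 value, or nothing if the subject stopped before Week 14 |
| MSFQ | Week 26/ET | Nothing |

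Where nothing is left, LOCF cannot supply a value, so the subject is also absent from the last-visit row.

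The schedule in force before Amendment 3 (Protocol Appendix 16) rated AIMS at every visit and MSFQ at Weeks 1, 2, 8, 26 and 52. Total loss therefore falls mainly on 26-week enrollers (CT-6.2.3 and CT-6.5.3).

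**How much drug remains at the cut**

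The documents give no residual-drug figure, so there is none to reproduce. The inputs come from Protocol 1.2.1:

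- Steady state, schizophrenia or schizoaffective disorder, 1-12 mg/day: "mean terminal elimination half-life at steady state was 95.4 and 89.3 hours, respectively" (brexpiprazole first, metabolite second).
- Single dose, healthy subjects: 48.3 to 80.8 h.
- Potent CYP3A4 or CYP2D6 inhibitors: "about a 1.5-fold increase in the terminal elimination half life of brexpiprazole". Hence 1.5 × 95.4 = 143.1 h.

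Fraction remaining = 2^(−t/half-life), and 7 days = 168 h. For example, 2^(−168/95.4) = 0.295 and 2^(−168/143.1) = 0.443.

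| Half-life | Day 7 | Day 10 | Day 14 |
|---|---|---|---|
| 48.3 h | 9.0% | 3.2% | 0.8% |
| 80.8 h | 23.7% | 12.8% | 5.6% |
| 95.4 h | 29.5% | 17.5% | 8.7% |
| 143.1 h | 44.3% | 31.3% | 19.6% |

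The stated accumulation factor of about 4 in healthy subjects gives a check on these inputs. Accumulation = 1/(1 − 2^(−24/half-life)) is 3.4 at 48.3 h, 5.4 at 80.8 h and 6.25 at 95.4 h. A factor of exactly 4 implies a half-life of 57.8 h and 13% remaining at day 7. The protocol gives no half-life for MDD subjects, so the range has to stay wide.

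**MSFQ recall**

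Every MSFQ item asks about the past month (Protocol Appendix 14; SAP 11.2.7). Taking a month as 30 days, a form completed d days after the last dose covers 30 − d days on treatment. That is 22 days at d = 8 and still 7 days at d = 23.

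**The case against.** The strongest reply is that the plan already limits the damage, and most of that reply stands. ET evaluations are due at withdrawal, so a late visit departs from what the protocol intends. Adverse events are the primary outcome. They are followed to 30 (+2) days, and EPS-related events and discontinuations are tabulated under SAP 9.1 without this cut. SAS and BARS normally retain an earlier on-drug rating. A 7-day on-treatment window is a legitimate choice for descriptive tables. The 30-day contact in Protocol 3.6.1.9 may be by telephone and schedules no scale.

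A reader might go further and infer that subjects who stop for EPS are the likeliest to attend late, so that the EPS-scale results are biased toward those who tolerated the drug. The documents do not support this. They do not relate the reason for stopping to the delay before the ET visit. For SAS and BARS, the retained rating is on drug and the excluded one is off drug, so dropping the late rating could raise the apparent effect as easily as lower it. Nor can a proportion of late visits be derived by supposing that leavers wait for the next scheduled visit, because Protocol 3.7.3 does not intend such a wait.

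A reader might also take 30-44% as the drug level typical of excluded ratings. It is the value at the cut, so every excluded rating lies below it. It also rests on the longest half-life in the protocol. The upper end could apply only to subjects on fluoxetine, paroxetine or duloxetine, the three of the six ADTs that the protocol names as CYP2D6 inhibitors.

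The reply does not answer the conflict between text and footnote, or the complete loss of MSFQ and of AIMS before Week 14.

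**Conclusion.** The point holds in a limited form. The text of SAP 11.1 and footnote b disagree on what is excluded. Under the Amendment 3/4 schedule, an ET visit more than 7 days after the last dose leaves no analysed post-baseline MSFQ, and no AIMS for a subject who stopped before Week 14.

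The day-7 residual is about 30% on the 95.4 h half-life, up to 44% with a potent inhibitor, and 9-24% on the single-dose half-lives. This assumes first-order decline and half-lives measured outside the MDD population. The MSFQ argument does not depend on residual drug: it needs only the one-month recall.

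The number of late ET visits is not given, so the size of any distortion cannot be computed, and its direction for SAS and BARS cannot be shown. The primary adverse-event analysis is unaffected. This is a cheap improvement to secondary safety summaries.

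**What to change.** 1. Reconcile the SAP 11.1 text with footnote b, stating which outputs the exclusion governs and to which visits it applies.
2. Keep the planned on-treatment rows unchanged.
3. Add a supplementary last-available row to CT-6.2 (AIMS) and CT-6.5 (MSFQ), and optionally to CT-6.1 (SAS) and CT-6.3 (BARS). It would include ratings made more than 7 and up to 30 (+2) days after the last dose. Report with it the number of late ratings and the days since last dose.

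No listing change is needed, since SAP Section 13 proposes no listings of these four scales.

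The cost is SAP wording and one row in two to four table sets, from data already collected. The downside is that the added row mixes on-drug and recently off-drug ratings and could dilute effects that ease after stopping. By day 30 only 0.5% (95.4 h) to 3.1% (143.1 h) of drug would remain, and an MSFQ completed then would cover essentially no treatment time. For that reason the row supplements the on-treatment row and does not replace it. If few subjects are affected, the counts will show it.

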11.2 Scales: Rules for Scoring and Handling of Missing Data

11.2.1 Clinical Global Impression (CGI)

CGI consists of two scales: CGI Severity (CGI-S), and CGI Improvement (CGI-I). CGI-S items are: 0 = not assessed, 1 = normal, not at all ill, 2 = borderline mentally ill, 3 = mildly ill, 4 = moderately ill, 5 = markedly ill, 6 = severely ill, 7 = among the most extremely ill patients. The score 0 (= not assessed) will be set to missing. The CGI-S is therefore a 7-point scale from 1 through 7.

CGI-I items are: 0 = not assessed, 1 = very much improved, 2 = much improved, 3 = minimally improved, 4 = no change, 5 = minimally worse, 6 = much worse, 7 = very much worse. The score of 0 (= not assessed) will be set to missing. The CGI-I is therefore a 7-point scale from 1 through 7. CGI improvement is judged with respect to the patient's condition at baseline.

11.2.2 Sheehan Disability Scale (SDS)

The Sheehan Disability Scale (SDS) is a self-rated instrument used to measure the effect of the patient's symptoms on work/school, social life, and family/home responsibilities. For each of the three items, scores range from 0 through 10. The number most representative of how much each area was disrupted by symptoms is marked along the line from 0 = not at all, to 10 = extremely. For the work/school item, no response was to be entered if the patient did not work or go to school for reasons unrelated to the disorder and a response therefore not being applicable. The Mean SDS Score will be calculated over the three item scores. All three item scores need to be available except for the work/school item score when this item is not applicable.

11.2.3 Inventory of Depressive Symptomatology (Self-Report) (IDS-SR)

The IDS-SR is a 30-item self-report measure used to assess core diagnostic depressive symptoms as well as atypical and melancholic symptom features of major depressive disorders. The IDS-SR consists of 30 items, all rated on a 0 to 3 scale with 0 being the “best” rating and 3 being the “worst” rating. Besides item 9, two sub-items 9A and 9B exist, with possible scores of 1, 2 or 3 for item 9A, and 0 or 1 for item 9B. The scores for these two sub-items are not included in the calculation of the total score. Item 11 or item 12 should be completed but not both, and similarly, item 13 or item 14 should be completed but not both. Should items 11 and 12 be rated both, then the maximum of the two scores will be used. The same approach will be used for handling items 13 and 14.

The IDS-SR Total Score is the sum of ratings of 28 item scores. The possible IDS-SR Total Score ranges from 0 to 84. The IDS-SR Total Score will be un-evaluable if less

than 23 of the 28 items are recorded. If the number of items recorded is at least 23 and at most 27, the IDS-SR Total Score will be the mean of the recorded items multiplied by 28 and then rounded to the first decimal place.

11.2.4 Simpson-Angus Scale (SAS)

The SAS is a rating scale used to measure EPS. The SAS is a 10-item scale, with each item rated from 0 to 4, with 0 being normal and 4 being the worst. The SAS Total score is the sum of ratings for all 10 items, with possible Total scores from 0 to 40. The SAS Total score will be unevaluable if less than 8 of the 10 items are recorded. If 8 or 9 of the 10 items are recorded, the Total score will be the mean of the recorded items multiplied by 10 and then rounded to the first decimal place.

11.2.5 Abnormal Involuntary Movement Scale (AIMS)

The AIMS is a 12-item scale. The first 10 items are rated from 0 to 4 (0=best, 4=worst). An item score of 0, depending on the item, either means: no abnormal involuntary movement (AIM), or no incapacitation due to AIM, or no awareness of AIM. An item score of 4 either means: severe AIM, or severe incapacitation due to AIM, or being aware of, and severe distress caused by AIM. Items 11 and 12, related to dental status, have dichotomous responses, 0=no and 1=yes. The AIMS Total Score is the sum of the ratings for the first seven items. The possible total scores are from 0 to 28. The AIMS Total Score will be unevaluable if less than 6 of the first 7 items are recorded. If 6 of the items are recorded, then the total score will be the mean of the recorded items multiplied by 7 and then rounded to the first decimal place.

11.2.6 Barnes Akathisia Rating Scale (Barnes)

The Barnes Akathisia Rating Scale will be used to assess the presence and severity of akathisia. This scale consists of 4 items. Only the 4th item, the Global Clinical Assessment of Akathisia, will be evaluated in this study. This item is rated on a 6-point scale, with 0 being best (absent) and 5 being worst (severe akathisia).

11.2.7 Massachusetts General Hospital Sexual Functioning Questionnaire (MSFQ)

The MSFQ is a measure of a patient's self-reported sexual functioning. The MSFQ includes 5 items, each addressing experiences over the last month: a) interest in sex, b) ability to get sexually aroused, c) ability to achieve orgasm, d) ability to get and maintain an erection, and e) overall sexual satisfaction. For items a) through e), a score of 1 indicates 'greater than normal', and 6 indicates 'totally absent'.

All item scores are analyzed separately. No total or mean score is derived.

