3.5.2.2 Safety Variables

In addition to AEs, safety variables to be examined in this trial will include physical examinations, vital signs, body weight, waist circumference, clinical laboratory tests (hematology, serum chemistry, urinalysis, and pregnancy tests), ECGs, the Simpson Angus Scale (SAS), the Abnormal Involuntary Movement Scale (AIMS), the Barnes Akathisia Rating Scale (BARS), the Columbia-Suicide Severity Rating Scale (C-SSRS), and the Massachusetts General Hospital Sexual Functioning Questionnaire (MSFQ).

Mean change from baseline and the incidence of potentially clinically relevant abnormal values will be calculated for vital signs, body weight, routine laboratory tests (including prolactin), and ECG parameters. Mean change from baseline will be calculated for coagulation parameters (prothrombin time [PT], activated partial thromboplastin time [aPTT], and International Normalized Ratio [INR]), glycosylated hemoglobin (HbA1c), thyroid-stimulating hormone (TSH), waist circumference, and body mass index (BMI; derived programmatically from body weight and height measurements). A central ECG service will be utilized to review all ECGs in order to standardize interpretations for the safety analysis. EPS will be evaluated by calculating mean change from baseline on the SAS, AIMS, and BARS. Sexual dysfunction will be evaluated as change from baseline in MSFQ score. The C-SSRS will be used to assess and classify reported suicidal behavior. By-patient listings of physical examination findings will be reviewed as a further assessment of safety.

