Appendix 14**Massachusetts General Hospital Sexual Functioning Questionnaire (MSFQ)**

Please answer all questions by circling the correct answer or the answer which seems the most appropriate to you (consider "normal" the time in your life prior to the past month when you were most satisfied with your sexual functioning).

a) How has your interest in sex been over the past month?

1	2	3	4	5	6
greater than normal	normal	minimally diminished	moderately diminished	markedly diminished	totally absent

b) How has your ability to get sexually aroused or excited been over the past month?

1	2	3	4	5	6
greater than normal	normal	minimally diminished	moderately diminished	markedly diminished	totally absent

c) How has your ability to achieve orgasm been over the past month?

1	2	3	4	5	6
greater than normal	normal	minimally diminished	moderately diminished	markedly diminished	totally absent

d) (for men only) How has your ability to get and maintain an erection been over the past month?

1	2	3	4	5	6
greater than normal	normal	minimally diminished	moderately diminished	markedly diminished	totally absent

e) How would you rate your overall sexual satisfaction over the past month?

1	2	3	4	5	6
greater than normal	normal	minimally diminished	moderately diminished	markedly diminished	totally absent

Copyright 1998, Depression and Clinical Research Program, Massachusetts General Hospital
(Derived from the Arizona Sexual Experiences Scale and from the Guided Interview Questionnaire by Segraves and Segraves).

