9.3 Physical Examination and Vital Signs Data

By-patient listings will be provided for physical examination. Summary statistics for changes from baseline in vital signs will be provided. Potentially clinically significant results in vital signs will also be summarized. In addition, the change from baseline in weight, BMI, and waist circumference, and potentially clinically relevant abnormalities in weight, will also be summarized by ADT and by Gender, separately.

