CT-6.4.5.3 Columbia-Suicide Severity Rating Scale (C-SSRS) - Listing of Treatment-emergent Suicidal Ideation – 26-Week Enrollers

CT-6.4.6.1 Columbia-Suicide Severity Rating Scale (C-SSRS) - Listing of Treatment-emergent Suicidal Behavior – All Subjects

CT-6.4.6.2 Columbia-Suicide Severity Rating Scale (C-SSRS) - Listing of Treatment-emergent Suicidal Behavior – 52-Week Enrollers

CT-6.4.6.3 Columbia-Suicide Severity Rating Scale (C-SSRS) - Listing of Treatment-emergent Suicidal Behavior – 26-Week Enrollers

CT-6.4.7.1 Columbia-Suicide Severity Rating Scale (C-SSRS) - Listing of Treatment-emergent Serious Ideation – All Subjects

CT-6.4.7.2 Columbia-Suicide Severity Rating Scale (C-SSRS) - Listing of Treatment-emergent Serious Ideation – 52-Week Enrollers

CT-6.4.7.3 Columbia-Suicide Severity Rating Scale (C-SSRS) - Listing of Treatment-emergent Serious Ideation – 26-Week Enrollers

CT-6.4.8.1 Columbia-Suicide Severity Rating Scale (C-SSRS) - Listing of Worsening Suicidal Ideation – All Subjects

CT-6.4.8.2 Columbia-Suicide Severity Rating Scale (C-SSRS) - Listing of Worsening Suicidal Ideation – 52-Week Enrollers

CT-6.4.8.3 Columbia-Suicide Severity Rating Scale (C-SSRS) - Listing of Worsening Suicidal Ideation – 26-Week Enrollers

CT-6.5.1 Summary of Mean Change in MSFQ Item Scores – All Subjects

CT-6.5.2 Summary of Mean Change in MSFQ Item Scores – 52-Week Enrollers

CT-6.5.3 Summary of Mean Change in MSFQ Item Scores – 26-Week Enrollers

CT-6.6.1 Incidence Rates in Resource Utilization – All Subjects

CT-6.6.2 Incidence Rates in Resource Utilization – 52-Week Enrollers

CT-6.6.3 Incidence Rates in Resource Utilization – 26-Week Enrollers

CT-7.1.1.1 Extent of Exposure – All Subjects

CT-7.1.1.2 Extent of Exposure – 52-Week Enrollers

CT-7.1.1.3 Extent of Exposure – 26-Week Enrollers

CT-7.1.2.1 Extent of Exposure by ADT – All Subjects

CT-7.1.2.2 Extent of Exposure by ADT – 52-Week Enrollers

CT-7.1.2.3 Extent of Exposure by ADT – 26-Week Enrollers

CT-7.1.3.1 Extent of Exposure to Each Dose per 4-Weekly Dosing Interval – All Subjects

CT-7.1.3.2 Extent of Exposure to Each Dose per 4-Weekly Dosing Interval – 52-Week Enrollers

CT-7.1.3.3 Extent of Exposure to Each Dose per 4-Weekly Dosing Interval – 26-Week Enrollers

CT-7.1.4.1 Extent of Exposure to Each Dose per 4-Weekly Dosing Interval by ADT – All Subjects

CT-7.1.4.2 Extent of Exposure to Each Dose per 4-Weekly Dosing Interval by ADT – 52-Week Enrollers

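### The MSFQ tables report only mean item change, without a split by sex or a count of new dysfunction, so a mean near zero could hide subjects who became dysfunctional

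*SAP*

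**What the plan says.** Protocol 3.5.2.2 gives the questionnaire its purpose: "Sexual dysfunction will be evaluated as change from baseline in MSFQ score". SAP 11.2.7 describes the instrument ("The MSFQ includes 5 items, each addressing experiences over the last month"), scores each item from 1 to 6, and rules out a total: "All item scores are analyzed separately. No total or mean score is derived". SAP 9.8 sets the type of summary: "Descriptive statistics will be provided for the SAS, AIMS, BARS, and MSFQ scales". The table list in SAP Section 13 has one MSFQ title, "Summary of Mean Change in MSFQ Item Scores", repeated for all subjects, 52-week enrollers and 26-week enrollers (CT-6.5.1 to CT-6.5.3). SAP 5.1 groups summaries by enrolment cohort and parent-study treatment. Sex is not a grouping there.

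The form in Protocol Appendix 14 marks the erection item as male only: "d) (for men only) How has your ability to get and maintain an erection been over the past month". SAP 11.2.7 lists that item without the restriction.

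The SAP does split other outcomes by sex. Changes in weight, BMI and waist "will also be summarized by ADT and by Gender, separately" (SAP 9.3), and TEAEs are tabulated for sex subgroups (SAP 9.1).

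**The concern.** A mean change answers whether the average subject moved. A safety reader also wants to know how many subjects developed a problem, and on this scale the two can differ. A score of 2 is normal, 1 is above normal, and 3 to 6 run from minimally diminished to absent, so the scale has room for movement in both directions.

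There is a plausible source of improvement in this population. Loss of interest in sex is itself a depression symptom on the IDS-SR (item 22, Protocol Appendix 9), so subjects whose depression lifts may improve on the MSFQ while others newly worsen.

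Pooling the sexes adds a second averaging step for items a, b, c and e. It also means that item d, answered by men, cannot be read beside male results for the other four items.

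Elsewhere the SAP counts subjects with emergent or marked change: emergent and worsening suicidality (SAP 9.5), new-onset QTc prolongation (SAP Table 9.4-1) and weight change of at least 7% (SAP Appendix 1). The MSFQ has no such count.

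**Working it through.** The documents give no MSFQ effect size, SD, threshold or test, so there is no planned figure to reproduce. The proportions, changes and sex shares below are assumptions that illustrate the mechanism.

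**1. Offsetting in the mean.** Mean change = sum of (proportion of subjects × change in score). Subjects not mentioned are unchanged.

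- 10% move from 2 to 4, nobody improves: 0.10 × 2 = +0.20.
- 10% move from 2 to 4, 20% move from 2 to 1: 0.10 × 2 + 0.20 × (−1) = 0.00.
- 10% move from 2 to 4, 10% move from 4 to 2: 0.10 × 2 + 0.10 × (−2) = 0.00.

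The third case needs no score of 1, only recovery in some subjects who were impaired at baseline. If the other 90% start at 2, a count of new dysfunction would show 10/90 = 11% of those normal at baseline, against a mean change of zero.

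**2. Pooling over sex.** Pooled mean = share of the affected sex × its mean change, with no change in the other sex. For a mean change of +0.40 in one sex:

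- share 30%: 0.30 × 0.40 = +0.12
- share 50%: 0.50 × 0.40 = +0.20
- share 70%: 0.70 × 0.40 = +0.28

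If both sexes change equally, pooling dilutes nothing.

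**3. Recall period.** Every item refers to the past month, for example "How has your interest in sex been over the past month". Taking a month as 30 days, the share of recall before the first open-label dose at study day D is (30 − D)/30, and zero from Day 30:

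| Study day | Pre-dose share |
|---|---|
| 7 (Week 1 target) | 23/30 = 77% |
| 14 (Week 2 target) | 16/30 = 53% |
| 16 | 14/30 = 47% |
| 21 | 9/30 = 30% |
| 50 (start of Week 8 window) | 0% |

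The current schedule (Protocol Table 3.6-1) collects the MSFQ at baseline and Week 26/ET only. The schedule before Amendment 3, shown in Protocol Appendix 16, also had it at Weeks 1, 2, 8 and 52/ET. Pre-dose recall therefore touches two sets of records: Weeks 1 and 2 of 52-week enrollers, and early-termination visits before about Day 30. The latter can supply the last-visit value. SAP 11.1 sets no minimum time on treatment.

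**The case against.** The SAP follows the protocol, which asks for change from baseline (3.5.2.2) and descriptive statistics (7.4.5). The primary outcome is AE frequency and severity (Protocol 3.5.1), and the MSFQ is one of many untested secondary safety measures. This stands: no rule is broken, and the point concerns how useful the tables are.

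Moves from 2 to 1 may be rare. The form anchors normal to the period when the subject was most satisfied with sexual functioning, so a score of 1 means better than that. This weakens the example in which 20% make that move, but not the one in which impaired subjects recover to 2.

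If an SD is reported, heterogeneity would show: the two zero-mean examples have SDs of √(0.4 + 0.2) = 0.77 and √(0.4 + 0.4) = 0.89. That is partly right, but an SD does not say how many subjects crossed from normal to diminished.

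Sexual dysfunction reported as an AE is counted as a TEAE, by sex (SAP 9.1, CT-8.2.2.3.1 to CT-8.2.2.3.3). That is a real safeguard. However, Protocol 5.2 elicits AEs with one general, non-leading question, and the MSFQ is the instrument that asks about sexual function directly.

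A reader might infer that the one-month recall undermines the MSFQ results, and that records before Day 30 should be dropped. The documents do not support this. Records from Week 8 on, including Week 26, lie wholly on treatment. Weeks 1 and 2 are separate rows under the SAP 11.1 windows, and from Day 16 less than half the recall is pre-dose. Time before Day 1 is also not untreated for everyone: the ADT continues, and the parent trials included brexpiprazole arms. Dropping these records would remove early discontinuers, possibly including those who left because of sexual side effects, from a safety table. It would also go against the protocol synopsis, which bases safety summaries on all available data.

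**Conclusion.** The point holds as a gap in reporting. With only pooled mean change per item, the planned tables can understate new sexual dysfunction, and they do not let item d be read beside male results for the other items. The illustrations range from a fully masked 10% (mean change 0.00) to a one-sex change of +0.40 shown as +0.12 to +0.28. All of these rest on assumed proportions.

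A reader might infer that new dysfunction will in fact be cancelled out. The documents cannot show that: it depends on how many subjects improve and on whether the sexes differ. Nor do they suggest that item d will be averaged over women, since the form restricts it to men. What the SAP lacks is a statement of that denominator. The recall issue is minor and needs a footnote.

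**What to change.** In CT-6.5.1 to CT-6.5.3, keep the mean-change summaries and:

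- Show every item by sex, and state that item d has men only in its denominator.
- Add, per item and by sex, n (%) of subjects moving from 2 or less at baseline to 3 or more, with those at 2 or less at baseline as denominator. This cut is the form's own boundary between normal and diminished. Neither document adopts it as a definition of dysfunction, so the SAP should state it explicitly.
- Add n (%) worsening among those already at 3 or more at baseline, so that further decline is counted too.
- Keep all records. Footnote that the one-month recall at Weeks 1 and 2 (52-week enrollers), and at early-termination visits before about Day 30, partly covers time before open-label dosing.

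The data are already collected. The cost is a few lines of SAP text and one extra table layout.
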